### 12.5.2. Sensitivity Analysis

Two separate sensitivity analyses will be completed on the primary endpoint, outlined below:

- 1) The primary effectiveness analysis will be repeated under the assumption that all subjects with missing endpoint data were successful.
- 2) The primary effectiveness analysis will be repeated under the assumption that all subjects with missing endpoint data were failures.
- 3) The primary effectiveness analysis will be repeated using multiple imputation for missing endpoint data. The covariates that may (list not all-inclusive) be included in the multiple imputation process are: age, gender, treated shoulder, arthritis diagnosis, Constant score (baseline and 12 month), and BMI.

#### 12.5.3. Pooling Data Analyses

A pooling analysis will be performed to assess the poolability of sites with respect to the primary endpoint measure. Success rates will be summarized by site, according to the primary analysis method. A Fisher's Exact Test will be used to test for a difference in composite success rate across sites. A significance level of 0.1 will be used to determine whether the sites are poolable. If a significant difference is found between sites, additional analyses will be done to identify factors that may be associated with this difference. Additionally, if a significant difference is observed, a random site adjusted estimate of the composite success rate, along with 95% CI, will be provided.

Although enrollment will be monitored in an effort to strive for even allocation between sites, those sites with less than five (5) evaluable subjects will be combined into a pseudo-site for purposes of analysis. To protect against having an overly large pseudo-site, when one pseudo-site exceeds five (5) evaluable subjects, a second pseudo-site will be formed. This process will continue as needed each time a pseudo-site exceeds five (5) evaluable subjects.

#### 12.6. Inferential Secondary Endpoints

The following secondary data will be evaluated for significant change from baseline to 24 months. Analyses will be performed on the ITT population, using all available data. The overall type I error will be controlled using the Hochberg method for adjusting for multiple comparisons, and will be tested only if the primary endpoint is met. Endpoints will be evaluated at a one-sided alpha level of 0.025.

- Constant score and Adjusted Constant score (see Section 12.6.1)
- American Shoulder and Elbow Surgeons (ASES) Score (see Section 12.6.2)
- Single Assessment Numeric Evaluation (SANE)
  - The SANE rating is determined by the by the subject's written response to the following question "How would you rate your shoulder today as a percentage of normal (0% to 100% scale with 100% being normal)?"

- EQ-5D (see Section 12.6.3)
- Pain (VAS)
  - Based on 0-10 scale
- Range of Motion
  - Forward Flexion
  - o Abduction
  - $\circ$  Internal rotation
  - External rotation
- Strength (average pull strength)
- Revision Rate

The hypothesis test for each of the above endpoints, with the exception of Pain (VAS) and revision rate, will be of the form:

H0:  $\mu \le 0$ HA:  $\mu > 0$ 

Where  $\mu$  is the mean change from baseline to 24 months (follow-up minus baseline) for that endpoint. The hypothesis test for the Pain (VAS) endpoint will be of the form:

H0:  $\mu \ge 0$ HA:  $\mu < 0$ 

Where  $\mu$  is the mean change from baseline to 24 months (follow-up minus baseline) in the VAS Pain score.

For each endpoint excluding revision rate, descriptive statistics will be provided for subjects at baseline and 24 month follow-up. The difference from baseline to 24 months will be summarized using descriptive statistics, and a paired t-test will be performed. Additionally, the 95% confidence interval will be calculated for the change from baseline.

The hypothesis test for the Revision rate will be of the form:

H0: p ≥ 13.2% HA: p < 13.2%

Where p is the proportion of subjects that had a revision in the 24 month time period. This endpoint was added based upon FDA feedback. As the sample size is already established at 133 subjects, the PG is based upon the observed revision rate from the Aequalis dataset and a non-inferiority margin of 8% that has approximately 90% power with a 1-sided alpha of 0.025 with the sample size of 133.

In the Aequalis historical control dataset, 10 of 191 subjects had a revision of some type within 24 months from surgery for an estimated revision rate of 5.2%. Using the same non-inferiority margin of 10%, a sample size of 100 is adequate to test with at least 90% power and a one-sided alpha of 0.025. Estimates for the revision rate at 24 months and an upper 97.5% confidence bound will be generated using a Kaplan-Meier time to event analysis. If this value is less than 13.2%, then the null hypothesis is rejected and it is concluded that the reivision rate is acceptable and not inferior to prior approved devices. Additional summaries

will include the proportion of subjects with a revision rate within 24 months along with a binomial two-sided 95% confidence limits.

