#### 7. Trial Hypotheses

The objective of the primary endpoint analysis is to demonstrate that the rate of the composite success endpoint in subjects with the Pyrocarbon HH is non-inferior to the rate observed in the Tornier Aequalis Post-Market Outcomes Study dataset. Formally, the hypothesis to be tested is:  $H_0: p \leq PG - \delta$ 

 $H_A: p > PG - \delta$ 

Where p is the proportion of subjects with a success for the composite success endpoint, PG is the performance goal, and  $\delta$  is the non-inferiority margin. The PG is derived from data for the Aequalis subjects with the appropriate indications and with two years of follow up data (or revision prior to two years). The PG and  $\delta$  being used for the hypothesis test take on the values of 0.85 (or 85%) and 0.10 (or 10%), respectively.

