### 9. Trial Design

This is a multi-center, prospective, single arm, investigational clinical study. The study will be conducted at up to 20 sites in the US. Each participating site will be encouraged to attempt implants in approximately 5 subjects in a 12 month time period, or until the enrollment limit is met. A subject is "enrolled" and count towards the enrollment limit of 190 subjects once the consent form is signed. A subject will count towards the limit of 157 subjects when inclusion/exclusion criteria are met (including unsuccessful and successful implantation of a PYC HH). Up to 157 subjects will have attempted implants with a Pyrocarbon HH to ensure at least 133 evaluable subjects are available for the primary endpoint analysis.

It is anticipated that this study will require approximately up to 24 months for subject enrollment. To ensure data are adequately distributed among sites and geographies, no more than 20% (n=31) of subjects may occur at a single site. Each site should attempt to implant 5 subjects within 12 months of activation. There is no minimum requirement for enrollments per site.

All enrolled subjects will be followed for at least 24 months (except for pre-operative screen failures). Study duration (first site activation to final subject follow-up) is expected to be approximately 4 years. If deemed necessary, subjects may be asked to return for additional visits beyond their final protocol visit to collect long-term data

Subjects who are enrolled and have a successful implant attempt (implant stable through wound closure) will have study assessments at 2 weeks, 3 months, 6 months, 12 months, 24 months, and annually thereafter (until the last implant attempt subject completes their 24 month visit) following surgery. Subjects will exit the study after the last implant attempt subjects completes their 24 month assessment unless it is determined, at the end of the study, to follow subjects long-term.

Subjects who are enrolled and have an unsuccessful implant attempt (attempt to implant the Pyrocarbon Humeral Head was not successful during the index procedure) will have annual post-op visits at 12 and 24 months in order to collect any available safety information. This also includes subjects who are excluded due to excessive glenoid reaming performed with the intent of implanting the Pyrocarbon Humeral Head. Subjects will exit the study after the 24 month assessments are complete.

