# 11.2. Missing Data and Censoring

The impact of missing data for the primary efficacy endpoint will be assessed by a sensitivity analysis. See the primary endpoint section for details.

No imputation for missing data will be performed on secondary endpoint data; i.e., patients missing the endpoint result at a visit or prematurely withdrawing prior to the time point at which the endpoint is measured will be excluded from the analysis of that endpoint.

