### **Revisions:**

A subject who has undergone a study system revision will be considered a failure for the primary efficacy endpoint. All available safety data will be included in summaries.

A revision is a procedure that adjusts or in any way modifies or removes part of the original implant configuration, with or without replacement of a component, after the initial surgery. A revision may also include adjusting the position of the original configuration. This may include removing a component of a joint implant and only replacing that single component. If a subject has revision surgery, the subject shall remain in the study and complete all required follow-up visits.

If a subject has a revision that includes permanent removal of the Pyrocarbon HH, they shall remain in the study and complete all required annual follow-up visits.

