# 12.2. Analysis Populations

The Intent-to-Treat (ITT) population will consist of all subjects who have undergone an attempted or successful implantation of the investigational system.

The Per-Protocol (PP) population will include all subjects who have undergone successful implantation of the investigational system, completed 24 months of follow-up, and have had no major protocol violations (defined as not meeting inclusion/exclusion criteria or not being consented properly). Major protocol violations (inclusion/exclusion criteria not met or consent issues) will be determined by the inclusion/exclusion and protocol deviation data sets.

Effectiveness analyses will be performed on the ITT population. Analysis of the PP population will be used in support of the ITT analyses of the primary efficacy endpoint. The safety analysis will be performed on the ITT population.

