### 12.5. Primary Effectiveness Analysis

### 12.5.1. Primary analysis

The primary endpoint is the rate of patient success at 24 months. A subject is a success at 24 months if:

- Their change in Constant score is  $\geq 17$  and
- They did not have revision surgery; and
- There is no radiographic evidence of system disassembly or fracture, and
- They did not have a system-related serious adverse event.

Subjects that undergo revision surgery within 24 months will be considered a primary endpoint failure at the time any component of the system is revised.

If a subject is missing the 24 month radiographic evidence assessment or Constant score component of the composite endpoint and did not have a system-related SAE or revision surgery, they will be excluded from the primary analysis due to inability to claim success or failure.

Subjects in whom an implant was attempted but the implant was unsuccessful will be included as failures in the primary analysis, regardless of the availability of 24 month radiographic evidence assessment or Constant score.

The presence of radiographic evidence of system disassembly or fracture will be assessed by independent radiologists. Discrepancies among the independent evaluations will be settled by majority rule. If the radiologists are unable to assess or the image wasn't available at 24 months, this will be considered missing data and the subject will be excluded from the primary analysis.

The non-inferiority of the test system to the performance goal will be evaluated using the 95% CI for the observed test system success rate. The study will be considered a success if the lower bound of the confidence interval is greater than 75% (85% - 10%).

The number of subjects who are successes (X) for each of the 4 individual components of the composite success endpoint, along with the number evaluated (N), will be summarized at 12 and 24 months as (X/N) and displayed with the overall success endpoint results based on data up to 12 and 24 months.

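### The SAP's revision-rate test has no rule for subjects who never received the head, and its Kaplan-Meier analysis conflicts with the exclusion of early withdrawals in SAP 11.2

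*SAP*

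**What the plan says.** **Population.** SAP 12.6 covers all inferential secondary endpoints, revision rate included, with one sentence: "Analyses will be performed on the ITT population, using all available data". SAP 12.2 defines ITT as "all subjects who have undergone an attempted or successful implantation of the investigational system".

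**Unsuccessful attempts.** SAP 9 keeps these subjects under observation: they "will have annual post-op visits at 12 and 24 months in order to collect any available safety information". For the primary endpoint the SAP deals with them explicitly (12.5.1): "Subjects in whom an implant was attempted but the implant was unsuccessful will be included as failures in the primary analysis". The revision test has no corresponding rule.

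**What a revision is.** The revisions paragraph that follows SAP 11.2 states: "A revision is a procedure that adjusts or in any way modifies or removes part of the original implant configuration".

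**The test.** SAP 12.6 sets the null at a revision proportion of 13.2% or more, from 10 revisions in 191 Aequalis subjects (5.2%) plus a margin of 8 points. The 24-month rate and its upper 97.5% bound come from a Kaplan-Meier analysis, and a bound below 13.2% rejects the null. A binomial summary is added.

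**Missing data.** SAP 11.2 gives one rule for all secondary endpoints: patients who lack the result, or those "prematurely withdrawing prior to the time point at which the endpoint is measured will be excluded from the analysis of that endpoint". It names no exception. The version history shows that the revision-rate endpoint came in with version 6.0.

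**The concern.** A subject who never received the head has no study configuration to revise, yet belongs to the analysis set and is seen at 12 and 24 months. Unless a rule says otherwise, that subject is in the risk set without an event throughout. A failed implantation then counts against the device in the primary analysis and in its favour in the revision test. Where such subjects exist, the direction is fixed: they can only lower the estimated revision rate.

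The second issue is a conflict between two instructions. A Kaplan-Meier analysis needs early withdrawals in the data, with unrevised ones censored and a revision before withdrawal kept as an event. SAP 11.2, taken at its word, takes early withdrawals out. The binomial summary has no method text of its own to set against 11.2.

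At stake is a formal claim: passing this test lets the sponsor conclude that the revision rate is acceptable and not inferior to that of earlier approved devices.

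**Working it through.** **Inputs from the SAP.** Null rate 13.2%; expected rate 10/191 = 5.2%; one-sided alpha 0.025; n = 133 for the power statement (12.6); 157 implant attempts and 15% attrition (10). The number of unsuccessful attempts and the number of revised subjects who withdraw are not given. Both are assumptions below.

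**The plan's own figure.** SAP 12.6 states about 90% power at n = 133. The arcsine formula gives Φ(2√133 × [asin√0.132 − asin√0.052] − 1.96) = Φ(2 × 11.533 × [0.3718 − 0.2301] − 1.96) = Φ(1.31) = 90.5%, so the figure reproduces. A z-test with null variance gives 87.8%, and an exact binomial test (pass at 9 or fewer of 133) gives 84.4%.

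**Part 1: unsuccessful attempts carried as revision-free.**

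Assume complete follow-up, so that the Kaplan-Meier estimate equals the simple proportion, and use the exact (Clopper-Pearson) upper 97.5% bound.

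1. With n = 157, 12 revisions give an upper bound of 12.97% (pass) and 13 give 13.74% (fail). The rule is to pass at 12 or fewer.
2. Let u of the 157 be unsuccessful attempts, and let the true rate among the 157 − u implanted subjects be 13.2%. The rate seen in ITT is 13.2% × (157 − u)/157.
3. The false-pass probability is P(X ≤ 12), with X binomial(157 − u, 0.132).

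| u (assumed) | Implanted | Rate seen in ITT | False-pass probability |
|---|---|---|---|
| 0 | 157 | 13.2% | 2.07% |
| 1 | 156 | 13.1% | 2.2% |
| 2 | 155 | 13.0% | 2.4% |
| 3 | 154 | 12.9% | 2.53% |
| 8 | 149 | 12.5% | 3.52% |
| 12 | 145 | 12.2% | 4.54% |

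Nominal 2.5% is reached at three unsuccessful attempts. With the implanted set alone the test stays within 2.5%: 1.84% for u = 8 and 2.44% for u = 12, where the pass limit is 11 revisions rather than 12. Part of the gap between these figures and the table comes from that one-event step, not from dilution.

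**Part 2: SAP 11.2 read literally.**

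If a share w_r of revised and w_u of unrevised subjects withdraw and all are dropped, the rate seen is p(1 − w_r) / [p(1 − w_r) + (1 − p)(1 − w_u)]. With w_r = w_u this equals p, so there is no bias, only lost data. With p = 13.2%, w_u = 15% and w_r = 30% (assumed) it is 0.0924/(0.0924 + 0.7378) = 11.1%.

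A borderline illustration, with assumed counts: 157 implanted, 24 withdrawals, 11 revisions.

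- Two of the revised subjects later withdraw. Kaplan-Meier on all 157 gives 7.6% with a log-log upper bound of 13.4% (fail). Literal 11.2 leaves 9/133 = 6.8% with a bound of 12.6% (pass).
- One revised subject later withdraws. Literal 11.2 gives 10/133 = 7.5% and a bound of 13.5%, slightly above the Kaplan-Meier bound.
- None does. Literal 11.2 gives 11/133 = 8.3% and a bound of 14.4%, which is worse for the device.

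With a linear bound, the two-withdrawal example passes either way (12.0% and 11.0%), so the reversal also depends on an interval type that the SAP does not name.

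**The case against.** **On unsuccessful attempts.** That they count as revision-free is a default consequence, not a stated rule. ITT is already narrow: intra-operative screen failures are identified before any attempt (Protocol 7.6.2, SAP 9), so only failures after an attempt has begun, such as excessive reaming, enter. The count may be zero, and with 0 to 2 the nominal 2.5% is not exceeded. Each unsuccessful attempt is also a primary-endpoint failure, and the revision test runs only if the primary endpoint is met. Finally, the choice of Kaplan-Meier interval alone moves the false-pass rate from 2.1% (log-log) to 3.8% (linear) with no unsuccessful attempts. All of this stands and limits the size of the problem. It does not supply the missing rule, and the penalty in the primary analysis does not remove the dilution in the revision estimate.

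**On withdrawals.** A reader might infer that the SAP plans to drop subjects already revised. The documents do not support that. The endpoint-specific text prescribes Kaplan-Meier, 12.6 calls for all available data, a revised subject is not missing the result, and both documents require revised subjects to stay in follow-up (Protocol 7.6.10; SAP revisions paragraph). A reader might also assume that 30% or 50% of revised subjects withdraw against 15% of the others. Simulation under 11.2 read literally then gives false-pass rates of 7.5% or 35%. Nothing in the documents points to such differential withdrawal, and with equal withdrawal the figure is 1.7%. What survives is that two instructions conflict and no text ranks them.

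**Conclusion.** The point holds as a gap in specification with a modest effect. In part 1 the direction is certain whenever unsuccessful attempts exist. At a true 13.2% among implanted subjects, the false-pass probability goes from 2.1% with none to 2.5%, 3.5% and 4.5% with 3, 8 and 12 of 157. These figures rest on assumed counts, complete follow-up and an exact bound in place of the unspecified Kaplan-Meier bound. If no attempt fails, there is no effect.

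Part 2 is an unreconciled conflict between SAP 11.2 and 12.6, not an established plan to discard revisions. Read literally, 11.2 would bias the result in the device's favour only if revised subjects withdraw more often than others. Otherwise it costs data and some power. The illustration shows that two revised withdrawals can decide a borderline result under a log-log bound.

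**What to change.** In SAP 12.6:

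- Define the revision-rate set as all subjects with a successful implantation.
- Set time zero at surgery.
- Count any revision within 24 months as an event, whatever the later follow-up.
- Censor unrevised subjects at last contact.
- Report the number of unsuccessful attempts beside the estimate, so that the restriction is visible.

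In SAP 11.2, state that the exclusion of early withdrawals does not apply to the revision rate, including its binomial summary. This would match the Aequalis cohort, in which subjects revised before two years were kept (SAP 7).

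The change is to SAP wording only, with no new data. The estimate becomes slightly less favourable and the set slightly smaller, both in proportion to the number of unsuccessful attempts.

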13.2 Primary Endpoint

The primary study endpoint will be compared for non-inferiority to a performance goal success rate of 85%. The Tornier Aequalis Post-Market Outcomes Study is the source of the data for the control group that was used to create the performance goal. Subjects with the appropriate indications with at least two years of follow up data (or revision prior to two years) were included in the cohort used to calculate the performance goal.

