### 13.1. Aequalis Data

A subset of data from the Tornier Aequalis Post-Market Outcomes Study was used to develop the performance goal for the primary endpoint hypothesis test of the current investigation. A total of 191 subjects from the post-market study had an indication similar to that of the current investigation and had endpoint status at 24 months determined. Their available data will be used in the comparison to the current investigation.

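### The 13.2% revision goal rests on a rate that omits unrevised subjects lost early, but the trial's Kaplan-Meier rate keeps them, so under non-informative loss the goal can only be too lenient or unchanged

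*SAP*

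**What the plan says.** **The goal.** SAP 12.6 tests whether the 24-month revision proportion is below 13.2%. The source rate is "10 of 191 subjects had a revision of some type within 24 months from surgery for an estimated revision rate of 5.2" per cent, to which the SAP adds "a non-inferiority margin of 8% that has approximately 90% power with a 1-sided alpha of 0.025 with the sample size of 133".

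**Who is in the 191.** SAP 13.1 says these subjects "had an indication similar to that of the current investigation and had endpoint status at 24 months determined". SAP 7 describes the source cohort as Aequalis subjects "with the appropriate indications and with two years of follow up data (or revision prior to two years"). Protocol 13.2 gives the same rule: subjects "with at least two years of follow up data (or revision prior to two years) were included in the cohort".

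**The trial's rate.** The 24-month estimate and its upper 97.5% bound "will be generated using a Kaplan-Meier time to event analysis", and the null hypothesis is rejected if that bound is below 13.2%. For the secondary endpoints, "Analyses will be performed on the ITT population, using all available data". SAP 12.2 defines ITT as every subject with an attempted or successful implantation.

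**What is not stated.** Neither document gives the number of indication-matched Aequalis subjects without 24-month status, or a Kaplan-Meier rate for Aequalis. The type of Kaplan-Meier bound is also missing. SAP 12.5.1 counts unsuccessful attempts as failures of the primary endpoint, but no rule says how they enter the revision analysis.

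**The concern.** The Aequalis inclusion rule treats early exits unequally. A subject revised at month 3 is counted. A subject who leaves unrevised at month 18 is not, although that subject contributed 18 event-free months. Dropping only the event-free early exits raises the observed proportion. A Kaplan-Meier estimate does not do this, because it credits each lost subject with the time observed.

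The same underlying risk can therefore give a higher figure in the source of the goal than in the trial. The comparison with 13.2% decides whether the device's revision rate is declared acceptable and no worse than that of earlier approved devices. The SAP added this test after FDA feedback. A threshold that can err in only one direction, in the device's favour, should not be left unexamined.

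**Working it through.** **1. Reproduce the goal.** 10/191 = 5.24%, and 5.24% + 8 points = 13.24%. The stated 13.2% reproduces.

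**2. Put the omitted Aequalis subjects back as censored.** The inputs are 10 revisions and 191 subjects (SAP 12.6 and 13.1). Assumptions, none of them in the documents: a share *d* of the full eligible cohort was left out, M = 191/(1 − *d*) − 191 subjects; the 10 revisions are evenly spaced over 24 months; losses fall at day 0, evenly, or just before 24 months. The 24-month rate is 1 − ∏(1 − 1/nᵢ), where nᵢ is the number at risk at revision *i*.

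| Share left out | M | Rate, even loss | Goal, even loss | Rate, late loss | Goal, late loss |
|---|---|---|---|---|---|
| 0% | 0 | 5.24% | 13.2% | 5.24% | 13.2% |
| 5% | 10 | 5.09% | 13.1% | 4.98% | 13.0% |
| 15% | 34 | 4.82% | 12.8% | 4.44% | 12.4% |
| 30% | 82 | 4.37% | 12.4% | 3.66% | 11.7% |

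A hand check at 15%: with late loss all 225 stay at risk, so 10/225 = 4.44%. With even loss each omitted subject counts about half, so 10/(191 + 17) = 4.81%, against 4.82% from the product. If every loss is at day 0, the rate stays 5.24% at any share. No row gives a goal above 13.2%.

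**3. The same mismatch seen from the trial.** Assumptions: 157 attempts, of which 24 are lost unrevised and evenly over time (the 15% attrition in SAP 10, leaving 133), and revisions evenly spaced. With G = Σ 1/[nᵢ(nᵢ − 1)] and S the 24-month survival estimate, the linear bound is 1 − S + 1.96·S·√G, and the log-log bound is 1 − S^exp(1.96·√G/|ln S|). The Aequalis rule gives k/133.

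| Revisions k | Kaplan-Meier | Log-log bound | Linear bound | k/133 | Log-log bound | Exact bound | Linear bound |
|---|---|---|---|---|---|---|---|
| 9 | 6.2% | 11.7% | 10.2% | 6.8% | 12.6% | 12.5% | 11.0% |
| 10 | 6.9% | 12.5% | 11.1% | 7.5% | 13.5% | 13.4% | 12.0% |
| 11 | 7.6% | 13.4% | 12.0% | 8.3% | 14.4% | 14.3% | 13.0% |
| 12 | 8.3% | 14.2% | 12.8% | 9.0% | 15.3% | 15.2% | 13.9% |
| 13 | 9.0% | 15.0% | 13.7% | 9.8% | 16.2% | 16.1% | 14.8% |

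Against 13.2%, the most revisions that pass with Kaplan-Meier and a log-log bound is 10. On the Aequalis rule it is 9, with a log-log or an exact bound. With linear bounds the counts are 12 and 11. Like for like, the difference is one revision.

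**4. Effect of moving only the goal.** In the step 3 scenario with the goal at 12.8% (15% left out, even loss), the log-log limit stays at 10, because 12.5% is below 12.8%. For the linear bound, 12 revisions is on the edge (12.83% against 12.82%). At 12.4%, the log-log limit falls to 9 and the linear limit to 11. Steps 3 and 4 are two views of one mismatch and must not be added.

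**The case against.** The strongest reply is that the trial's estimator is sound. In a simulation with a true 24-month rate of exactly 13.2%, 157 attempts and 15% even loss, the Kaplan-Meier estimate averages 13.2%. The log-log test passes wrongly about 1.8% of the time, inside the 2.5% allowed. The linear bound passes wrongly about 4.5% of the time, but that comes from the bound type. The rate on the Aequalis rule averages 14.2%. So a failure at 10/133 beside a Kaplan-Meier pass does not show that the trial analysis is wrong. This stands: any leniency lies in the goal, and the Aequalis rule should not become the deciding analysis.

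The direction also depends on non-informative loss. If lost Aequalis subjects were revised elsewhere, 10/191 could understate their risk. The documents cannot exclude that.

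The SAP offers partial cover. It plans a binomial revision proportion with two-sided 95% limits (12.6) and a qualitative comparison with Aequalis and the literature (12.7). But the denominator of the proportion is not given, and neither analysis decides the test. The endpoint is secondary, is tested only if the primary is met, and revision already counts as failure in the primary composite. That limits the weight of the point but does not remove the mismatch.

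**Conclusion.** The mismatch of bases is established from the documents. Under non-informative loss, 13.2% is too high or unchanged. How much too high cannot be determined, because the number of excluded Aequalis subjects is not reported. At an assumed 15% left out, the excess is 0 to 0.8 points, or about 0.4 with even loss. That is small beside the 8-point margin. The trial-side equivalent is about one revision where roughly 9 to 12 would pass.

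A reader might infer four stronger things that the documents do not support:

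- **That the test is shown to be too lenient.** If nobody was left out, or all losses were at day 0, the goal does not change.
- **That the Aequalis rate is from completers only.** The cohort also keeps anyone revised before two years. That selective rule is what can raise the rate.
- **That the gap is 9 against 12 revisions.** This sets an exact binomial bound beside a linear Kaplan-Meier bound. Most of the gap comes from the bound type.
- **That unsuccessful attempts are kept in the risk set and dilute the rate.** These subjects have no study head to revise, so keeping them would lower the estimate. But the SAP does not say how they are handled, and their number is unknown.

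**What to change.** 1. Compute the Aequalis 24-month revision rate by Kaplan-Meier on all indication-matched Aequalis subjects, with those lost unrevised before two years censored when they left. Set the goal as that rate plus 8 points, and report how many subjects had been excluded.
2. Keep Kaplan-Meier on ITT as the deciding analysis. State how unsuccessful attempts enter it, and add a sensitivity analysis restricted to successfully implanted subjects.
3. Name the type of confidence bound in SAP 12.6. In the scenario above it changes the passing count by two (10 against 12), more than the mismatch does.
4. If the Aequalis loss data cannot be recovered, report the trial on the Aequalis rule (revised, or 24-month status known) as a sensitivity analysis beside the Kaplan-Meier test. If the two disagree, qualify the conclusion that revision is no worse than with earlier approved devices.

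The cost is one re-analysis of a post-market study that carries the sponsor's name, a few SAP sentences, and a threshold that may become slightly stricter. The documents do not show whether follow-up dates for the lost Aequalis subjects exist, which is why step 4 is needed.
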